Title:

Young Adults' Responses to E-Cigarette Advertisement Features and the Effect of Restricting Features on Tobacco Use - Phase 2

NCT: NCT05207033**Date:** 4/3/2025

Study Protocol:
RESEARCH DESIGN
R00 Phase: Aim 2:

Participant Recruitment and Screening. We will recruit 150 young adults susceptible to EC use to complete the study. Participants will be recruited from the greater Worcester area using email, flyers, and social media, advertising an opportunity to participate in a health messaging study. Inclusion criteria are as follows: 1) 18 years old, 2) fluent in English (earn a score of at least 4 on the Rapid Estimate of Adult Literacy in Medicine), 3) biochemically confirmed abstinence of alcohol (breath alcohol concentration=.00) and combusted tobacco or marijuana (eCO: exhaled carbon monoxide <6 parts per million) at time of visit, and 4) reporting never trying an e-cigarette, not even a puff. Susceptibility to EC use, will be determined using the Susceptibility to Use Tobacco Products questionnaire.¹³

In the R00 Phase, I will use the knowledge gained in the K99 to determine the highest impact features of the selected EC ads. The highest impact features will be determined by a host of variables including features that receive the greatest visual attention (determined by eye-tracking), orienting response (determined by deceleration of heart rate), and arousal (determined by increased skin conductance). Self-report measures will be considered as well including ads associated with increased acceptance, higher positive attitudes, decreased EC severity, and increased behavioral intentions. From this information, I will create two conditions of advertisements: 1) regulated advertisements and 2) unregulated advertisements. Regulated advertisements will be the same 15 advertisements as Study 1 but with the omission of the high impact features as a way to simulate effects that may occur in young adults if these high impact features were restricted by the FDA. Unregulated advertisements will be kept in their true form with no manipulation. Using an RCT, I will track participant changes over 6 months in the following measures: susceptibility, severity, behavioral intentions, and actual tobacco use behavior following exposure to EC ads.

Participant Screening and Recruitment. Participants will be screened and recruited in the same fashion as Study 1. If participants meet eligibility, they will be scheduled for a visit. The inclusion criteria will remain the same as in Study 1. The sample will include young adults who are susceptible to using ECs.²⁰ To account for an anticipated attrition rate of 20%, 150 participants will be recruited to ensure a sample of 120 participants. *Note: Participants will be offered information about the Massachusetts Tobacco Cessation and Prevention Program (MTCP).*

Retention. All participants will receive \$5 per visit to offset travel costs to and from the study site for a total of 4 visits (\$20), \$25 for each visit that they attend (\$100), and an additional \$1 for each time they open the online magazine and answer the survey questions (\$24), for a total of \$168. We will also facilitate study visits by offering evening and weekend appointments as well as additional retention strategies (e.g., multiple sources of contact, reminder calls/emails/texts). These methods are consistent with our team's previous studies and have resulted in excellent retention rates.

Procedures. Following confirmation of eligibility criteria and demonstration of participants' informed consent, participants will come to the lab for a baseline visit and complete sociodemographic questions and measures pertaining to tobacco use susceptibility,²⁰ perceived severity of using ECs,²¹ motivations to avoid ECs,²² behavioral intentions,²³ exposure to tobacco advertising,^{24,25} and receptivity to tobacco advertising.²⁶ Participants will also receive a tutorial on how the online magazine will work. Then, participants will be randomized in a 1:1 ratio to one of two conditions using a computer-generated sequence: 1) Regulated condition in which all features that are highest impact have been removed or 2) Unregulated condition in which all features remain in the advertisements. Research staff will be blinded to condition allocation. Advertisements will be the same as in Study 1 but manipulated for the regulated condition. Every week, for 24 weeks, participants will be instructed to view a 10-page online magazine

delivered via email that includes content and articles aimed at young people from popular magazines among young adults, such as ESPN Magazine and Marie Claire that often contain EC ads.⁷ Before viewing, participants will be asked about their exposure to tobacco advertising in the last week and their receptivity to advertising as well as other masking questions. Every magazine will also contain two EC ads and two ads for products other than tobacco. During viewing, time spent on the ad page will be recorded. Every week, the online magazine will contain different content. Additionally, EC ads will be repeated at times. Opening and reading of the online magazine will be validated using recall tasks and incentives. At the one month, three month, and six month marks, participants will come into the lab and be assessed for tobacco use susceptibility,²⁰ perceived severity,²¹ motivations to avoid ECs,²² behavioral intentions to use EC, and recall of the ads.²³ Participants will also be asked about their tobacco use, including ECs²⁴ and bio-markers of EC use, in addition to eCO to confirm self-reported combusted tobacco use status. See Study 2 Flow Chart.

Measures. Sociodemographic data will assess participant age, sex, marital status, ethnicity, employment status, occupation, years of education, and socioeconomic status. Time spent on ad will be measured by a timer that records the amount of seconds a participant spends on the EC ad through REDCap. Tobacco use questions including pictures to enhance recall will assess tobacco use across all tobacco products (i.e., cigarettes, cigars, cigarillos, little cigars, hookah, pipe tobacco) including ECs.²⁴ Tobacco use susceptibility, including ECs susceptibility of use will be measured using the 27-item measure.²⁰ Perceived severity of using ECs will be assessed by participants' perceived significance, severity, and seriousness of health threats from EC use.²¹ Motivation to avoid ECs including importance, confidence, and readiness to avoid ECs will be collected to assess for changes in motivations.²² Behavioral intentions²³ will be evaluated using questions like "How interested are you in trying ECs?" and "How willing are you to try ECs?" Participants will also complete the PhenX Toolkit measure of participants' exposure to tobacco advertising^{24,25} and tobacco advertising receptivity, a validated measure of tobacco promotional product influence.²⁶ Biochemical confirmation of tobacco non-use will be conducted with salivary cotinine (~3 day nicotine biomarker).

Power Analysis. Trial of EC products is the primary outcome of the study; thus estimated power will be based on this outcome at the 6-month follow-up. No direct data is available on which to base sample size estimates. The closest estimates for the trial of EC products among unregulated and regulated groups are based on a study conducted by [name] (co-mentor) examining EC trial rates at 6-month follow-up (7.9% vs. 4.7% respectively) among young adults who were exposed vs. not exposed to 4 EC ads at a single time point.⁵ Since participants will be shown 24 ads over 6 months, we estimate that the trial of EC products after viewing EC advertisements over multiple time points will be higher in both the unregulated (24%) and regulated (6%) groups. As such, 150 participants (75/group) will be enrolled in the study. The sample size will provide 80% power to detect an 18% difference in increased trial of EC products between unregulated and regulated groups for a two-sided .05 level chi-squared test. Our estimates of sample size adjust for attrition rates of 20% in each arm. These attrition rates are a conservative estimate based on [name] (co-mentor) previous research. We are confident that with a total sample size of 150 participants (n = 120 after accounting for attrition), we will have adequate power to test our primary aim. It is important to note that this sample size is deliberately conservative, as it does not assume the availability of repeated outcome measures that will be taken throughout the study. By choosing models that utilize longitudinal data, we will be increasing the power to detect differences between arms. Note: We are currently running a trial that will help us work out any unforeseen issues with the study and sample size, but are basing these estimates on the best available data⁵ and most conservative estimates.

Data Analytic Plan. Baseline demographics and EC attitudes, intentions, and use will be summarized by groups as appropriate. Continuous variables will be presented as mean±SD and

compared among the 2 groups using ANOVA test. Categorical variables will be presented as counts and proportions and compared among the 2 groups using the chi-squared test. EC trial and use, at baseline and 6-month follow-up, will be compared between the 2 groups using logistic regression analysis. The GEE model will be performed for the repeated measure analysis of EC attitudes, intentions, and use across multiple visits. Self-reported exposure and receptivity to other tobacco advertising will be used as a covariate in the analyses.

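### E-cigarette trial, the primary outcome, is asked only at lab visits, with no remote fallback for a missed month-6 visit, so an unknown part of the planned 20% loss is avoidable.

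*Combined protocol and SAP*

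**What the plan says.** **Outcome.** Power Analysis states: "Trial of EC products is the primary outcome of the study", and "estimated power will be based on this outcome at the 6-month follow-up".

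**How it is collected.** Procedures: "At the one month, three month, and six month marks, participants will come into the lab and be assessed for" susceptibility, perceived severity, motivation, intentions and ad recall. The next sentence adds questions on tobacco use including ECs, biomarkers of EC use, and exhaled carbon monoxide to confirm combusted tobacco status. Measures describes the tobacco-use questions as supported by pictures. It adds salivary cotinine, with a window of about 3 days, to confirm non-use.

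**Loss allowed for.** Participant Screening and Recruitment: "To account for an anticipated attrition rate of 20%, 150 participants will be recruited to ensure a sample of 120 participants". Power Analysis uses the same figures.

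**Existing remote contact.** Procedures describes an emailed magazine each week for 24 weeks, preceded by questions on ad exposure, ad receptivity and masking items. No EC-trial item is listed there. Measures shows that REDCap is already in use: time on each ad comes from "a timer that records the amount of seconds a participant spends on the EC ad through REDCap". Retention offers payments, evening and weekend appointments, several contact routes, and reminders by call, email and text. It says nothing about collecting outcomes remotely when a visit is missed.

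**Analysis.** Data Analytic Plan compares EC trial and use at 6 months by logistic regression, with GEE for repeated measures. It gives no rule for a missing month-6 answer and does not say whether a positive answer at month 1 or 3 counts.

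**The concern.** Whether someone has tried an e-cigarette in the past six months can only be learned by asking. A marker with a window of about 3 days cannot verify a single trial months earlier, and exhaled carbon monoxide addresses combusted products. The lab is needed for the biomarkers, not for the question.

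As written, a participant who still opens the magazine at week 24 but cannot come to the lab has no month-6 answer, although the study has a working online channel to that person. The expected number of events is small, so each lost answer matters. A person who has started vaping might also be less willing to attend a visit with breath and saliva tests, in which case events would be lost more often than non-events.

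**Working it through.** **Inputs.** From Power Analysis: 24% (unregulated) vs 6% (regulated), 75 enrolled per arm, 20% attrition, and the test, "for a two-sided .05 level chi-squared test". Recovery fractions and selective-loss rates are not in the documents and are assumptions here.

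**1. The plan's own figure.** Evaluable per arm: 75 × 0.80 = 60. With pooled rate p̄ = 0.15,

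power = Φ{[0.18√60 − 1.96√(2 × 0.15 × 0.85)] / √(0.24 × 0.76 + 0.06 × 0.94)} = Φ{(1.394 − 0.990) / 0.489} = Φ(0.828) = 0.796.

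This reproduces the claim, "The sample size will provide 80% power to detect an 18% difference". The 20% loss is already paid for in the sample size: 60 / 0.80 = 75.

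**2. Power if some missing outcomes are recovered (assumption).** Exact power is the sum of the binomial probabilities of all tables for which the uncorrected Pearson test gives p < 0.05, at 24% vs 6%. Half of 15 missing per arm is 7.5, so 60 + 7.5 is taken as 67. Three quarters gives about 71.

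| Share of missing recovered | n per arm | Exact power |
|---|---|---|
| None | 60 | 0.814 |
| Half | 67 | 0.859 |
| Three quarters | 71 | 0.880 |
| All | 75 | 0.899 |

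The normal approximation shows the same pattern, from 0.796 at 60 to 0.878 at 75.

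**3. Selective loss, same in both arms (assumption).** Triers miss the visit at 40%, non-triers at 15%.

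- Unregulated: retained 0.24 × 0.60 + 0.76 × 0.85 = 0.144 + 0.646 = 0.790; observed rate 0.144 / 0.790 = 18.2%.
- Regulated: retained 0.06 × 0.60 + 0.94 × 0.85 = 0.036 + 0.799 = 0.835; observed rate 0.036 / 0.835 = 4.3%.
- Missing: 21% and 16.5%, close to the planned 20%. Evaluable: 75 × 0.790 ≈ 59 and 75 × 0.835 ≈ 63.
- Risk difference: 18.2 − 4.3 = 13.9 points, against a true 18.
- Odds ratio: true (0.24/0.76) / (0.06/0.94) = 4.95; observed (0.144/0.646) / (0.036/0.799) = 4.95.
- Exact power with 59 and 63 evaluable at these rates: about 71%.

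**4. When the odds ratio would be biased.** The observed odds ratio equals the true one times the ratio, unregulated to regulated, of (trier retention / non-trier retention). When both arms have 0.60/0.85, the ratio is 1. If only the unregulated arm lost triers selectively and the regulated arm lost 15% of everyone, the odds ratio would become 4.95 × (0.60/0.85) / (0.85/0.85) = 3.49. The documents give no information on whether loss would differ by arm in this way.

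**The case against.** Several arguments on the other side have weight.

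- **The 20% is a planning allowance.** Power Analysis calls it conservative and builds it into the sample size. A reader might infer that the stated power is wrong; step 1 shows that it is not.
- **Not all loss comes from the visit mode.** A reader might infer that lab-only collection causes the whole 20%. Attrition also includes people who withdraw or stop responding, whom a link would not recover. The documents give no split, so no recovery fraction can be claimed.
- **Selective loss need not bias the planned analysis.** A reader might infer that losing more triers biases the primary estimate. The planned model is logistic, and loss that depends on outcome but not on arm leaves its odds ratio unchanged. What suffers is the risk difference, which is the scale of the power statement, and power.
- **Trial is cumulative.** Participants enter never having tried an EC, so a positive answer at month 1 or 3 settles ever-trial even if month 6 is missed. This stands, but the plan does not say that such answers count, and an earlier negative leaves later trial unknown.
- **The lab visit has a purpose.** Biomarkers are part of the assessment, and remote responders would go unconfirmed. If non-attenders are more often triers, confirmation is absent where it is most wanted. This is a real trade-off, limited by the roughly 3-day window, which cannot verify six-month trial in attendees either.
- **Retention is already addressed.** The payments, appointment times and reminders aim to bring people to the lab; they do not provide for those who still do not come. The Study 2 flow chart is not reproduced in the text available, so any detail given only there could not be checked.

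**Conclusion.** The point holds as an avoidable weakness in how the primary outcome is ascertained. It is not an error in the sample size. EC trial is asked only at lab visits as written, no fallback is described, and the study already surveys participants online each week.

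The possible power gain is modest: from 81% to 86% if half of the missing outcomes were recovered, with a ceiling of 90% if none were lost. If triers stayed away more often, equally in both arms, power could fall to about 71% at the assumed 40% vs 15%, and the risk difference would shrink by 4.1 points with the odds ratio intact. All of these figures rest on the plan's assumed 24% vs 6%, and the recovery and loss rates are illustrations. Bias in the odds ratio would need a loss mechanism that differs by arm, which the documents neither state nor rule out.

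The case for acting is that the remedy is cheap and the trial is small: at 60 per arm the plan expects about 14 events against 4 (60 × 0.24 = 14.4; 60 × 0.06 = 3.6).

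**What to change.** Add to Procedures and the Data Analytic Plan:

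1. For anyone who does not attend within the month-6 visit window, send the same EC-trial and tobacco-use questions, with their pictures, by REDCap link, followed up through the reminder contacts already planned.
2. Define the primary outcome as ever-trial by month 6. Count lab answers, remote answers, and any positive report at month 1 or 3. An earlier negative with no month-6 answer remains missing.
3. Record the mode of each answer, and tabulate by arm how many outcomes come from each source and how many remain missing.
4. Keep biomarkers for attendees, and report the primary result with and without remote answers.

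Sending the questions only after a missed visit adds no EC-use item to the weekly surveys, so their masking is unaffected.

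**Cost.** One REDCap form, a few sentences of protocol text, and some staff time for reminders; no extra visits. The downsides are a second mode of answering and no biomarker confirmation for remote responders, which the analysis without remote answers makes visible.

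### The primary comparison of EC trial at month 6 has no rule for people who miss that visit, so trial already reported at month 1 or 3 can fall out of it

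*Combined protocol and SAP*

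**What the plan says.** The Power Analysis section fixes the outcome and its time point: "Trial of EC products is the primary outcome of the study; thus estimated power will be based on this outcome at the 6-month follow-up". The Data Analytic Plan gives the method: "EC trial and use, at baseline and 6-month follow-up, will be compared between the 2 groups using logistic regression analysis".

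Procedures schedules three follow-up assessments, "At the one month, three month, and six month marks, participants will come into the lab", and at these visits "Participants will also be asked about their tobacco use, including ECs". Trial can therefore be on record at month 1 or 3 for someone who never returns.

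Attrition is handled through enrolment. Participant Screening and Recruitment says "To account for an anticipated attrition rate of 20%, 150 participants will be recruited to ensure a sample of 120 participants", and Power Analysis says "Our estimates of sample size adjust for attrition rates of 20% in each arm". The document defines no analysis set, gives no missing-data method, and does not say whether trial is cumulative over visits.

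Power Analysis also says that models using the longitudinal data will raise power. The only longitudinal model named in the Data Analytic Plan is a GEE for attitudes, intentions and use. The sentence before it lists trial and use as separate items, so it is unclear whether the GEE covers trial.

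Eligibility requires "reporting never trying an e-cigarette, not even a puff", and Participant Screening and Recruitment adds "The inclusion criteria will remain the same as in Study 1".

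**The concern.** First trial in never-users cannot be undone. Once reported, it is known whether or not the person attends month 6. A month-6 comparison among attenders ignores that information. Few events are expected: 60 × 0.24 = 14.4 and 60 × 0.06 = 3.6 among completers, so one to three lost events are a noticeable share. If people who have tried an EC are also more likely to leave, the attenders' rates are too low as well. With no rule stated, the choice would be made after the data are seen.

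Two smaller matters sit in the same text. The general claim of a longitudinal power gain has no model clearly attached to the primary outcome. The baseline logistic comparison has no events in either arm.

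**Working it through.** **Inputs from the document.** 24% unregulated and 6% regulated at 6 months; two-sided 5% chi-squared test; 75 per arm enrolled, 60 per arm after 20% attrition; visits at months 1, 3 and 6; no prior EC trial at entry.

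**Assumptions, not in the document.** Constant hazard of first trial unless stated; the month-6 question captures trial to date; unadjusted tests. Powers below are from simulation, 40,000 runs per scenario (Monte Carlo standard error about 0.2 point), except where a formula or exact enumeration is given.

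**1. The plan's own figure.** Mean rate 0.15, n = 60 per arm:

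z = [0.18 − 1.96 × √(2 × 0.15 × 0.85 / 60)] / √[(0.24 × 0.76 + 0.06 × 0.94) / 60] = (0.18 − 0.1278) / 0.0631 = 0.828, which gives power of 79.6%.

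Exact enumeration of the uncorrected chi-squared test gives 81.4%. The stated 80% reproduces.

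**2. Trial known at each visit.** Cumulative trial by month t is 1 − (1 − p)^(t/6):
- unregulated: 4.5%, 12.8% and 24% at months 1, 3 and 6
- regulated: 1.0%, 3.0% and 6%

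**3. Events left out under 20% dropout unrelated to trial.** Attenders contribute 75 × 0.8 × (0.24 + 0.06) = 18.0 events.
- *All dropout after month 3:* 15 people per arm leave with known status, so 15 × (0.128 + 0.030) = 2.4 events are lost from 20.4 known.
- *Dropout spread over visits:* the chance of leaving at each visit is 1 − 0.8^(1/3) = 7.2%, so 0.928, 0.862 and 0.800 remain. Known events are 75 × (0.0447 × 0.928 + 0.0835 × 0.862 + 0.1118 × 0.800) = 15.2 unregulated, and 3.8 regulated by the same sum. The total is 19.0, so 1.0 is lost.

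**4. Power, 75 per arm enrolled.**

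| Dropout pattern | Known events | Lost if only attenders count | Power, attenders | Power, grouped log-rank |
|---|---|---|---|---|
| All before month 1 | 18.0 | 0 | 82% | 82% |
| Spread over visits | 19.0 | 1.0 | 82.0% | 83.9% |
| All after month 3 | 20.4 | 2.4 | 82.1% | 86.4% |
| Each visit missed independently, 20% | 20.0 | 2.0 | 82.3% | 85.9% |
| Spread; reported triers 3 times as likely to leave (assumption) | 19.0 | 2.9 | 77.9% | about 84% |

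In the last row, attenders who have tried in the unregulated arm are 0.0447 × 0.928 × 0.785² + 0.0835 × 0.862 × 0.785 + 0.1118 × 0.800 = 0.171 of those randomised, where 0.785 = 1 − 3 × 0.0717. Attending non-triers are 0.76 × 0.8 = 0.608. The rate in attenders is 0.171 / (0.171 + 0.608) = 22.0%. Cumulative incidence to the last attended visit gives 24.0%.

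**5. Do repeated visits help by themselves?** With complete follow-up at 60 per arm, across three hazard shapes, the month-6 chi-squared test has 81.2% to 81.9% power and the grouped log-rank 81.7% to 82.4%. The gain is under 1 point. Any larger gain comes from keeping events reported before dropout.

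**6. Why not simply count any-visit trial in the logistic model?** Under spread dropout, 15.2 / 75 = 0.203 of the unregulated arm has a known event.
- Excluding people lost without an event: 0.203 / (0.203 + 0.608) = 25.0%.
- Counting them as non-triers: 20.3%.

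Neither recovers 24%. If dropout were 30% versus 10% by arm (assumption) with true rates equal at 15%, type I error is:
- 5.0% to 6.8% when they are excluded
- 5.1% to 8.0% when they count as non-triers
- 4.9% to 5.1% in month-6 attenders
- 4.7% to 5.0% with the log-rank test

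**7. Baseline.** The comparison is 0/75 versus 0/75. A binomial model returns an arm standard error of 35,273, meaning no finite estimate exists.

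**The case against.** The strongest reply is that the effect is small on the plan's own inputs. With dropout unrelated to trial, month-6 attenders give unbiased rates and about 82% power. That stands.

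A reader might infer that an open rule lets the result swing, since the unregulated rate could be reported anywhere from 20.3% to 25.0%. That is a one-arm figure. Under spread dropout the odds ratio, which the planned model estimates, is 4.95 in attenders, 4.96 with any-visit trial excluding those lost, and 4.78 counting them as non-triers, a move of under 4%. The risk difference moves more (18.0, 18.7 and 15.2 points), mainly through counting people as non-triers.

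A reader might also infer that triers will drop out more and that the study is therefore underpowered. No passage says so, and the size depends on how such dropout is defined. If triers leave at three times the rate whether or not their trial was reported first, normal-approximation power in attenders is 64.5%, not 77.9%, and part of that loss cannot be recovered from earlier visits.

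Nor is it certain that earlier trial is discarded. The GEE for use across visits may capture it, though the text does not make that the primary analysis. Finally, Power Analysis says that the sample size does not rely on repeated measures, so the power-gain sentence changes no design number.

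**Conclusion.** The gap is real and worth fixing, but modest. The plan compares the primary outcome at month 6, collects the same information at months 1 and 3, and states no rule for people who miss month 6. On the natural reading, about 1 to 2.4 of 19 to 20 known events would be left out, with 82% power where 84% to 86% is available. There is no loss if all dropout precedes month 1. Power in attenders falls below 80%, to about 78% against 84%, only under the assumed threefold dropout among reported triers, which also lowers the unregulated rate to 22%.

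These figures assume 24% and 6%, a constant hazard, unadjusted tests and a month-6 question that captures trial to date. The document does not give that question's wording. The sample size is not at fault, and the baseline defect does not touch the month-6 test.

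**What to change.** - Define the primary outcome as first EC trial reported at the 1-, 3- or 6-month visit.
- Analyse it with a discrete-time logistic model, which can carry the planned advertising covariate, or with a grouped log-rank test. Follow each person to the last attended visit and report 6-month cumulative incidence by arm.
- Keep the planned month-6 logistic model in attenders as a sensitivity analysis. Do not make primary an any-visit logistic model that excludes people lost without an event or counts them as non-triers.
- State how people with no follow-up visit are handled, and how trial first reported after a skipped visit is dated.
- Delete the baseline time point from the logistic sentence and report baseline trial as 0 by eligibility.
- Minor: say whether use in the GEE includes trial, and limit the power-gain sentence to attitudes and intentions, or say that for EC trial any gain depends on dropout and is not quantified.

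The cost is a few sentences and a little more analysis work. No extra participants, visits or procedures are needed. Bias remains if people miss a visit because they have just tried an EC. If trial triples the chance of missing that same visit (assumption), the unregulated rate is 19.3% in attenders and still only 20.9% with earlier visits used.

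### The 80% power is stated for a chi-squared test, but 6-month EC trial is analysed by logistic regression on about 18 expected events with no test of the group effect named; Firth-penalised regression would close the gap cheaply

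*Combined protocol and SAP*

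**What the plan says.** The Power Analysis section fixes the outcome and time point: "Trial of EC products is the primary outcome of the study; thus estimated power will be based on this outcome at the 6-month follow-up". It assumes that trial rates "will be higher in both the unregulated (24%) and regulated (6%) groups", and states: "The sample size will provide 80% power to detect an 18% difference in increased trial of EC products" between the groups, "for a two-sided .05 level chi-squared test". On numbers it says that "150 participants (75/group) will be enrolled in the study" and "Our estimates of sample size adjust for attrition rates of 20% in each arm", which leaves 120 completers, or 60 per arm.

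The Data Analytic Plan then uses a different method for this outcome: "EC trial and use, at baseline and 6-month follow-up, will be compared between the 2 groups using logistic regression analysis". Its last sentence adds self-reported exposure and receptivity to other tobacco advertising as covariate adjustment. Chi-squared tests appear there only for comparing categorical variables in the group summaries.

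Neither section names the test of the group coefficient (Wald, score, likelihood-ratio, penalised or exact), and neither says what happens if an arm has few or no events.

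One inclusion criterion also bears on the point: "reporting never trying an e-cigarette, not even a puff".

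**The concern.** With plentiful events the usual tests from a logistic model agree with each other and with the chi-squared test, and naming one is a formality. Here events are few, and the tests differ both in power and in how well they keep to the 5% level. The stated 80% therefore belongs to one test, while the analysis may use another. If the choice is left until the data are in, it can decide significance. With 60 per arm and one event in the regulated arm, the likelihood-ratio test rejects from 6 unregulated events, Pearson from 7 and Wald from 8.

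A further problem is separation. If nobody in the regulated arm tries an EC, ordinary maximum-likelihood logistic regression has no finite estimate of the group effect, and its Wald p-value is meaningless however large the difference between arms.

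**Working it through.** **Inputs (Power Analysis).** Rates 24% and 6%; two-sided 0.05; 75 per arm enrolled; 20% attrition, so 75 × 0.80 = 60 per arm.

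**The plan's own figure.** For the two-proportion test with pooled variance under the null, mean rate (0.24 + 0.06)/2 = 0.15:

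power = Φ{[0.18 − 1.96 × √(2 × 0.15 × 0.85/60)] / √[(0.24 × 0.76 + 0.06 × 0.94)/60]} = 79.6%.

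Exact enumeration of the uncorrected chi-squared test gives 81.4%. The stated 80% is reproduced.

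**Expected events.** 60 × 0.24 + 60 × 0.06 = 14.4 + 3.6 = 18.0. With group, exposure and receptivity as three terms, that is 18/3 = 6 events per term.

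**Exact power by test.** All 61 × 61 outcomes of two independent Binomial(60, p) arms were enumerated for the unadjusted two-arm logistic model. Wald is log OR divided by its standard error, with a zero cell counted as non-significant. Firth is the penalised likelihood-ratio test, which in this model amounts to adding 0.5 to each cell. The unregulated rate is held at 24%.

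| Regulated rate | Pearson | Wald | Likelihood-ratio | Firth | P(no regulated events) = (1 − p)^60 |
|---|---|---|---|---|---|
| 6% | 81.4% | 77.4% | 84.0% | 81.1% | 2.4% |
| 5% | 87.3% | 81.0% | 89.2% | 86.9% | 4.6% |
| 4% | 92.2% | 81.7% | 93.5% | 91.7% | 8.6% |
| 3% | 95.8% | 78.2% | 96.6% | 95.3% | 16.1% |
| 2% | 98.2% | 67.3% | 98.6% | 97.8% | 29.8% |

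Wald trails Pearson by 4.0 points at 6%, about 6 at 5% and about 10 at 4%. At 4.7%, the rate the plan cites for young adults not exposed to EC ads, the chance of no regulated-arm events is 5.6%.

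**Exact type I error, 60 per arm.**

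| Common rate | Pearson | Wald | Likelihood-ratio | Firth |
|---|---|---|---|---|
| 6% | 4.7% | 0.9% | 7.3% | 3.1% |
| 15% | 4.7% | 4.3% | 5.8% | 4.6% |
| 24% | 5.2% | 4.7% | 5.3% | 4.7% |

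**Separation, worked case.** For 0/60 versus 14/60, Fisher's p is 0.00005. One standard logistic routine stopped with a singular matrix; another returned a standard error of about 16,900 and p = 0.999. The Firth statistic, with 0.5 added per cell, is

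2 × [14.5 ln(14.5/61) + 46.5 ln(46.5/61) + 0.5 ln(0.5/61) + 60.5 ln(60.5/61) − 15 ln(15/122) − 107 ln(107/122)] = 18.2 on 1 degree of freedom, p = 0.00002.

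**Covariates.** The documents give no covariate effects, so adjusted power cannot be derived from them. A simulation with two covariates of assumed effect kept the same pattern at 24% versus 6%: Wald about 77%, likelihood-ratio about 83%, Firth about 81%.

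**The case against.** The strongest reply is that the plan never names a Wald test. In an unadjusted two-arm logistic model the score test is the Pearson chi-squared test, so powering on chi-squared and analysing by logistic regression is common practice and not in itself a contradiction. Depending on the unnamed test, power is 77.4%, 81.4% or 84.0%. That stands: a reader might infer that the planned analysis has 77% power, but the documents support this only if default Wald output is used.

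A reader might also infer that power falls steadily as the regulated arm does better. It does not. Wald power rises from 77.4% at a 6% regulated rate to 81.7% at 4%. It drops back below 80% at about 3%, where at 78.2% it is still above its value at 6%, and is clearly lost only at about 2%. The plan assumes 6%, and rates of 2 to 3% lie below even the unexposed rate it cites.

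The shortfall is also small beside the uncertainty in the inputs. Lowering 24% to 23% takes Pearson power from 81.4% to 77.8%, and the plan admits that it has no direct data for these rates. About 2.4 of the points lost by Wald come from samples with no regulated events being scored as non-significant. Wald's severe conservatism, and most of the likelihood-ratio inflation, belong to the low common rate; at 15% they are modest.

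This limits the size of the point but does not remove it. Nothing in the plan steers the analyst away from Wald, and the likelihood-ratio test is not a clean alternative because it exceeded 5% at every common rate tabulated. Wald trails Pearson and Firth at every regulated rate tabulated, and separation has a real, if modest, probability at the plan's own rate.

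**Conclusion.** The point holds as a mismatch between the test that was powered and an analysis whose test is unnamed, in a setting where the choice matters. If Wald output is used, unadjusted power at the design point is about 77%, against about 81% for Pearson or Firth. The gap to Firth is about 4 points at a 6% regulated rate and about 17 at 3%. There is a 2.4% chance (5.6% at a 4.7% rate) of a result that the ordinary model cannot test. These figures assume 60 completers per arm, the plan's 24% in the unregulated arm and no covariate adjustment.

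The documents do not support saying that the trial is underpowered: the 80% is reproduced for the test it names and survives under a suitable logistic method. This is a cheap improvement, not a flaw in the design.

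The baseline comparison of EC trial is a separate, harmless slip. The never-tried criterion makes EC trial zero in both arms at entry, so no logistic model can be fitted there. The 6-month comparison is unaffected.

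**What to change.** In the Data Analytic Plan, state that EC trial at 6 months is compared between groups by Firth-penalised logistic regression with the stated covariates, using the penalised likelihood-ratio test for the group effect and a profile-likelihood confidence interval for the odds ratio. In the Power Analysis, state power for that test: about 81% unadjusted at 24% versus 6% with 60 per arm. As a minor tidy-up, remove the baseline time point from the logistic comparison of EC trial.

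This takes a sentence or two and standard software, with no new data and no change in sample size. It gives a usable estimate and test when an arm has no events, and type I error stayed below 5% at the common rates tabulated (3.1% to 4.7%). The downside is slight shrinkage of the odds ratio toward 1.
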